4.0 OVERALL STUDY DESIGN

This is a Phase 2, multi-center, double-masked, randomized, placebo-controlled clinical study. Subjects will be randomized to one of the following treatment arms at Visit 2 (Day 1):

- Low dose ST-100 Ophthalmic Solution: [REDACTED]
- High dose ST-100 Ophthalmic Solution: [REDACTED]
- Placebo Ophthalmic Solution (Vehicle): [REDACTED]

Approximately 150 subjects will be randomly assigned to one of the three groups (1:1:1) to receive either ST-100 Ophthalmic Solution or placebo solution as topical ophthalmic drops administered bilaterally BID for 4 weeks. Subjects, Sponsor, Contract Research Organization (CRO), and site personnel will be masked to treatment assignment.

[figure not shown]
During the 7-day study run-in period prior to randomization, all subjects will receive Placebo Ophthalmic Solution (Vehicle) bilaterally BID.

[figure not shown]
During the screening period, two 90-minute exposures to the CAE® will be conducted to ascertain eligibility to enter the study at Visit 1 (Day -7 ± 1) and Visit 2 (Day 1). Subjects who qualify after the initial screening visit will enter the run-in phase, where they will self-administer vehicle BID for approximately 7 days. Those who qualify at Visit 2 (Day 1) will be randomized to receive study drug in a double-masked fashion for 28 days. Subjects will self-administer drops BID and will complete daily diary assessments as instructed.

The CAE® exposure will occur at Visit 1 (Day -7 ± 1), Visit 2 (Day 1), Visit 5 (Day 8 ± 1), Visit 6 (Day 15 ± 1), and Visit 7 (Day 29 ± 2), with Pre-CAE®, during CAE® and Post-CAE® assessments of ocular signs and symptoms.

At Visit 3 (Day 2 ± 2 h) and Visit 4 (Day 4 ± 2 h), no CAE® exposure will occur but signs and symptoms will be assessed for 24h recovery post-CAE® and 72h recovery post-CAE®. Study drug will be discontinued at Visit 7. Subjects will exit from the study at this visit.

The total number of expected participants, including screen failures, is approximately 300 subjects. A study design flow chart is provided below:

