9.3 PROCEDURES FOR REPORTING SERIOUS ADVERSE EVENTS

All SAEs and their outcomes, regardless of causality or expectedness, must be reported to Ora and the Sponsor as required by the IRB/IEC, federal, state, or local regulations and governing health authorities and recorded on the appropriate case report form (CRF). Adverse events will be collected after the signing of the Informed Consent).

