### 9.2 Missing or Inconclusive Data Handling

Imputation of missing data will be executed for partial or missing dates where complete dates are required to flag data as treatment-emergent or concomitant with treatment. Partial/missing start and end dates for AEs and concomitant medications will be imputed as follows:

Partial/missing start date:

25OCT2021

Confidential & Proprietary

Page 14 of 15

- Dates with missing day only will be imputed as the 1st of the month unless the month and year are same as the month and year of first dose of study medication, in which case missing day will be imputed as the first dose day of study medication.
- Dates with both day and month missing will be imputed as 1 Jan unless the year is same as the year of first dose of study medication, in which case missing day and month will be imputed as the first dose day and month of study medication.
- Completely missing dates will be imputed as the first dose date of study medication unless the end date is on or before the first dose date of study medication, in which case missing date will be imputed as 1 Jan of the same year as the end date.

Partial/missing end date:

- Dates with missing day only will be imputed as the last day of the month unless the month and year are the same as the month and year of the last dose of study medication, in which case missing day will be imputed as the last dose day of study medication.
- Dates with both day and month missing will be imputed as 31 Dec unless the year is same as the year of the last dose of study medication, in which case missing day and month will be imputed as the last dose day and month of study medication.
- If the ongoing flag is missing or “Yes” then the date will not be imputed unless death date is available, in which case the missing date will be imputed as the death date. If ongoing is “No” then the missing end date will be imputed as the last dose date.
- If the imputed date is after the date of death, then the end date will be set equal to the date of death.

The original dates will be displayed in data listings and the imputed dates will be used in derivations only (study day, treatment-emergence status, etc).

Missing data for the primary efficacy endpoints will be imputed using multiple imputation on the ITT population as specified in Estimand 1 for primary analyses.

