### 12.2 Concomitant Medications

Concomitant medications will be coded using World Health Organization Drug Dictionary (WHODrug) Global (B3, March 2021) and summarized to the therapeutic drug class (Anatomical Therapeutic Chemical [ATC] 4 classification) and preferred name. If the ATC 4 classification is not provided, then the next lowest classification that is provided in the coding dictionary will be used. The preferred name will be defined as the active ingredient; if the active ingredient is not provided or includes more than two ingredients (e.g., multivitamins), then the drug name will be summarized as the preferred name. Any uncoded terms will be summarized under the ATC classification and preferred name of “Uncoded.”

Concomitant medications are defined as those medications listed as having been taken (1) prior to initiation of randomized study drug administration and continuing for any period of time following the first administration of randomized study drug or (2) at any time following the first administration of randomized study drug. Prior medications are defined as those listed as having been prior to initiation of randomized study drug administration but not taken for any instance following the first administration of randomized study drug.

Listings of concomitant medications will be generated separately for ocular and non-ocular data.

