### 16.1 Adverse Events

An AE is defined as any untoward medical occurrence associated with the use of an IP in humans, whether or not considered IP-related. An AE can be any unfavorable and unintended sign (e.g., an abnormal laboratory finding), symptom, or disease temporally associated with the use of an IP, without any judgment about causality. An AE can arise from any use of the IP (e.g., off-label use, use in combination with another drug or medical device) and from any route of administration, formulation, or dose, including an overdose. An AE can arise from any delivery, implantation, or use of a medical device, including medical device failure, subject characteristics that may impact medical device performance (e.g., anatomical limitations), and therapeutic parameters (e.g., energy applied, sizing, dose release, and anatomic fit) associated with medical device use. All AEs will be coded using the MedDRA 24.0.

Treatment-emergent adverse events (TEAE) are defined as any event that occurs or worsens on or after the first dose of randomized study drug..

Severity of an AE is defined as a qualitative assessment of the degree of intensity of an AE as determined by the Investigator or reported to him/her by the subject. The assessment of severity is made irrespective of relationship to study drug or seriousness of the event and should be evaluated according to the following scale:

- *Mild*: Event is noticeable to the subject, but is easily tolerated and does not interfere with the subject's daily activities.
- *Moderate*: Event is bothersome, possibly requiring additional therapy, and may interfere with the subject's daily activities.
- *Severe*: Event is intolerable, necessitates additional therapy or alteration of therapy, and interferes with the subject's daily activities.

The relationship of each AE to the IP should be determined by the investigator using these explanations:

- *Definitely Related*: Relationship exists when the AE follows a reasonable sequence from the time of IP administration, follows a known response pattern of the drug class, is confirmed by improvement on stopping the IP and no other reasonable cause exists.
- *Probably Related*: Relationship exists when the AE follows a reasonable sequence from the time of IP administration, follows a known response pattern of the drug class, is confirmed by improvement on stopping the IP and the suspect IP is the most likely of all causes.

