- *Possibly Related*: Relationship exists when the AE follows a reasonable sequence from the time of IP administration, but could also have been produced by the subject's clinical state or by other drugs administered to the subject.
- *Unlikely to be Related*: Relationship uncertain to the investigational product. Likely to be related to factors other than investigational product but cannot be ruled out with certainty.
- *Not Related*: Concurrent illness, concurrent medication, or other known cause is clearly responsible for the AE, the administration of the IP and the occurrence of the AE are not reasonably related in time, or exposure to IP has not occurred.

TEAEs that are recorded as definitely related, probably related, and possibly related are considered as treatment-related TEAEs.

The expectedness of an AE should be determined based upon existing safety information about the IP using these explanations:

- **Unexpected**: An AE that is not listed in the Investigator's Brochure (IB) or is not listed at the specificity or severity that has been observed.
- **Expected**: An AE that is listed in the IB at the specificity and severity that has been observed.
- **Not applicable**: An AE unrelated to the IP.

All AEs that are mentioned in the IB as occurring with a class of products or as anticipated from the pharmacological/mechanical (or other) properties of the product but are not specifically mentioned as occurring with the particular product under investigation are to be considered unexpected

An overall summary will be presented that includes the number of events and the number and percentage of subjects who experienced at least one AE, ocular AE, and non-ocular AE by treatment group and overall subjects. This summary will also include the number of events and the number and percentage of subjects who experienced at least one TEAE, as well as breakdowns of TEAEs further categorized as ocular or non-ocular, TEAEs by severity, TEAEs by relationship to study drug, TEAEs causing premature treatment discontinuation, and SAEs. TE-SAEs will also be categorized as ocular or non-ocular, TE-SAEs by severity, TE-SAEs by relationship to study drug, TE-SAEs causing premature treatment discontinuation, and TE-SAEs leading to death.

Summaries will be provided for the following categories of AEs:

- Ocular and non-ocular TAEs by SOC and PT
- Ocular and non-ocular TAEs by SOC, PT, and maximal severity
- Ocular and non-ocular treatment-related TAEs by SOC and PT

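### The partial start-date rules in SAP 9.2 ignore a known end date, so an adverse event that ended in the run-in can be counted as treatment-emergent; separately, the onset-day table has no category after Day 29

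*SAP*

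**What the plan says.** SAP 9.2 has three rules for incomplete AE and concomitant-medication start dates:

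- **Day missing:** first of the month, or the first-dose date if month and year match the first dose.
- **Day and month missing:** 1 January, unless the year matches the first dose, "in which case missing day and month will be imputed as the first dose day and month of study medication".
- **Completely missing:** the first-dose date, "unless the end date is on or before the first dose date of study medication". In that case it becomes 1 January of the end-date year.

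The section adds that "the imputed dates will be used in derivations only (study day, treatment-emergence status, etc". SAP 16.1 defines a TEAE as "any event that occurs or worsens on or after the first dose of randomized study drug", and its overall summary counts "subjects who experienced at least one TEAE".

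Events from before randomization are in the database. Protocol 9.3 says: "Adverse events will be collected after the signing of the Informed Consent". Protocol 4.0 says: "During the 7-day study run-in period prior to randomization, all subjects will receive Placebo Ophthalmic Solution (Vehicle) bilaterally BID".

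The onset-day table in SAP 16.1 has three categories: up to Day 8, after Day 8 through Day 15, and after Day 15 through Day 29. Visit 7 is Day 29 ± 2 days in Protocol 4.0, Protocol 8.3.8 and SAP Table 1, but ± 1 day in the Protocol synopsis.

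**The concern.** Imputing an uncertain start to the first-dose date is sound when the event could have begun on treatment. A recorded end before the first randomized dose rules that out: the event can neither occur nor worsen on or after that dose. SAP 9.2 recognises this only for the record with the least information. If nothing is known about the start, an event that ended in the run-in is not a TEAE. If the month or year is known, the same event gets a start later than its own end and is a TEAE.

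Such a record would enter the TEAE summaries by subject, class, term, severity and relationship. The same rules govern medications: one stopped before the first dose can be given a start on that date, although SAP 12.2 treats a drug as prior when it was taken before randomized treatment "but not taken for any instance following the first administration of randomized study drug".

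The onset table has a different gap. The TEAE definition has no upper day limit, and AEs are queried at Visit 7 both before and after the CAE exposure (Protocol 8.3.8). A TEAE starting on Day 30 or 31 would appear in the other TEAE tables but in no row of this one.

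**Working it through.** The documents give no figure to reproduce. The check applies the rules as written.

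**Inputs.** The three start-date rules (SAP 9.2), the TEAE definition and onset categories (SAP 16.1), and the Visit 7 windows (Protocol synopsis, 4.0, 8.3.8; SAP Table 1). Assumptions: *study medication* in SAP 9.2 means randomized study drug; illustrative first randomized dose F = 20 Jul 2021 and last dose 17 Aug 2021.

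**Rule.** An event is flagged TEAE if its imputed start ≥ F. The corrected rule uses the first of the known month, or 1 January of the known year, when a complete recorded end < F.

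| Recorded start | Recorded end | Start as written | TEAE as written | Corrected start | TEAE corrected |
|---|---|---|---|---|---|
| Jul 2021 | 16 Jul | 20 Jul (4 days after end) | yes | 1 Jul | no |
| Jul 2021 | 19 Jul | 20 Jul (1 day after end) | yes | 1 Jul | no |
| 2021 | 16 Jul | 20 Jul (4 days after end) | yes | 1 Jan | no |
| 2021 | 19 Jul | 20 Jul (1 day after end) | yes | 1 Jan | no |
| completely missing | 16 or 19 Jul | 1 Jan | no | unchanged | no |
| Jul 2021 or 2021 | 20 Jul (first-dose day) | 20 Jul | yes | unchanged | yes |
| Jul 2021 or 2021 | 28 Jul | 20 Jul | yes | unchanged | yes |
| partial | Jul 2021 (imputed 31 Jul) | 20 Jul | yes | unchanged | yes |

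The first four rows are wrong as written and right after the correction.

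**Dependence on the calendar.** A first dose late in the month makes every day-missing example match. To remove that choice, take every first-dose date from 1 Jun to 30 Sep 2021 (122 dates, assumed) and every start/end pair inside a run-in of g days, which is g(g+1)/2 pairs per date.

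| Run-in g | Records | Flagged, day missing | Flagged, day and month missing | Flagged, completely missing |
|---|---|---|---|---|
| 6 days | 122 × 21 = 2,562 | 2,198 (85.8%) | 2,562 (100%) | 0 |
| 7 days | 122 × 28 = 3,416 | 2,856 (83.6%) | 3,416 (100%) | 0 |
| 8 days | 122 × 36 = 4,392 | 3,576 (81.4%) | 4,392 (100%) | 0 |

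The day-missing records that escape are those starting in the previous calendar month. The percentages describe what the rule does to a run-in AE that already has a partial start and a complete end. They are not expected frequencies.

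**Does the correction behave?** Over all 365 first-dose dates in 2021 and a 7-day run-in (365 × 28 = 10,220 records per rule), the corrected rules leave 0 starts after the end and 0 TEAE flags. Events that start and end on Days 1–29 (365 × 435 pairs × 2 rules = 317,550 records) show 0 changes, as they must, because none ends before F.

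**Onset categories.** SAP 4.1 makes Day 1 the day of randomization, with no Day 0. The latest permitted Visit 7 is 29 + 1 = Day 30 or 29 + 2 = Day 31. Uncovered days: Day 30 under ± 1; Days 30 and 31 under ± 2.

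**The case against.** **Scope sentence.** SAP 9.2 opens by limiting imputation to records that need a complete date to be flagged. If a recorded end precedes the first dose, no start date is needed, so such a record could be read as exempt. The reading is possible, but the completely-missing rule itself imputes records that ended before the first dose. The exemption is therefore unclear, and a programmer following the bullets would produce the misflag.

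**Reference dose.** *Study medication* is not defined in SAP 9.2. SAP 12.2 and 16.1 say randomized study drug, which supports that reading without proving it, and Protocol 8.3.3 uses study drug for the drops taken before Visit 2. If the run-in vehicle were meant, the error would reverse: partial dates would move to the start of run-in, before randomization. This stands as a limit on the claim and is a further reason to name the dose.

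**Rarity and direction.** A run-in AE with a complete end but a partial start should be uncommon, because AEs are queried at Visits 1 and 2 and onset dates must be documented. An event about a week old for which only the year is known is hard to imagine. The misflag also over-counts TEAEs, and original dates stay in the listings. All of this stands and keeps the point minor.

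**Onset bands.** Days 8, 15 and 29 are the planned days of Visits 5, 6 and 7, so the bands may be meant as nominal visit intervals. The SAP nevertheless defines them by study day of onset, and a day beyond the last limit has no row.

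**Conclusion.** The concern holds in both parts, as a minor point. Read literally, the two partial-date rules give a start after the recorded end and a TEAE flag to an AE that ended before randomized treatment, in four of four worked examples. This rests on reading *study medication* as randomized study drug, and it applies only when the known month and year, or the known year, match the first dose. The onset table leaves one day uncovered under the ± 1 window and two under ± 2; Day 30 is uncovered either way. The number of affected records cannot be estimated from the documents and is probably small. Only safety tables and medication classification are touched; no effect on efficacy and no bias between arms is claimed.

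**What to change.** 1. **SAP 9.2, both partial-date start rules.** Add: if a complete recorded (not imputed) end date is strictly before the first dose of randomized study drug, impute the first of the known month (day missing) or 1 January of the known year (day and month missing). Other records keep the existing imputation. *Strictly before* matters: the first randomized dose is given under supervision at Visit 2 (Protocol 8.3.3), and a reaction that resolves the same day must remain a TEAE.
2. **SAP 9.2, reference dose.** Write randomized study drug throughout, matching SAP 12.2 and 16.1.
3. **SAP 16.1.** Make the last onset category open-ended: after Day 15.
4. **Visit 7 window.** Reconcile ± 1 day in the Protocol synopsis with ± 2 days in Protocol 4.0, Protocol 8.3.8 and SAP Table 1.

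The cost is a few words and minor reprogramming before database lock. Two things remain. A run-in AE whose end date is also partial would still be flagged, which is the cautious direction. The completely-missing rule would still treat an event ending on the first-dose day as not treatment-emergent, unlike the partial-date rules; that difference is already in the SAP and could be settled in the same edit.

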### 9.3 Definition of Baseline

Baseline measures are defined as

## 9.4 Data Analysis Conventions

All data analysis will be performed by SDC after the study is completed and the database has been locked and released for unmasking. Statistical programming and analyses will be performed using SAS® version 9.4 or higher. Output will be provided in rich text format (RTF) for tables and portable document format (PDF) for tables, listings, and figures using landscape orientation. All study data will be listed by subject, treatment, and visit (as applicable) based on all randomized subjects unless otherwise specified.

Summaries for continuous and ordinal variables will include the number of observations (n), arithmetic mean, standard deviation (SD), median, minimum, and maximum. Minima and maxima will be reported with the same precision as the raw values; means and medians will be presented to one additional decimal place than reported in the raw values. Standard deviations will be presented to two additional decimal places than reported in the raw values. Summaries for discrete variables will include counts and percentages. All percentages will be rounded to one decimal place (i.e., XX.X%). Differences between active treatment groups and placebo will be calculated as active minus placebo and change from baseline will be calculated as follow-up visit minus baseline.

Unless otherwise specified, summaries will be presented by treatment group and, where appropriate, visit. Listings will be sorted by treatment group, subject number, visit/time point, and parameter as applicable.

## 9.5 Adjustments for Multiplicity

A 2D grid of 100 black rectangles on a white background. Each rectangle is outlined in red and has a small white square at its top-left corner. The rectangles are arranged in a grid pattern with varying widths and heights, creating a stepped effect. The top row has 10 rectangles, the second row has 9, and so on down to the bottom row which has 1 rectangle.

## 10. Disposition of Subjects

Subject disposition will be presented in terms of the numbers and percentages of subjects who were included in the following analysis populations: [REDACTED]

Subjects who are not discontinued from the study will be considered study completers. Disposition will be summarized by

The total number of screened subjects with the number and percentage of screen failure subjects.

The reasons for premature study discontinuation will be summarized by treatment group for all discontinued subjects. Percentages will be calculated using discontinued subjects as the denominator. The reasons for study discontinuation that will be summarized include: AE, protocol violation, administrative reasons, sponsor termination of study, subject choice, lost to follow-up, lack of efficacy, and other. The subset of COVID-19-related discontinuations will be summarized as well. A subject listing will be provided that includes the date of and reason for premature study discontinuation. The listing will indicate COVID-19 relatedness with a reason for COVID-19 relatedness.

25OCT2021

Confidential & Proprietary

Page 17 of 18

For all screen failures, the reasons for screen failure will be displayed with the percentages calculated using total number of screen failures as the denominator.

In addition, subject listings will be provided that include informed consent date, screen failure reason, and exclusions from analysis populations. Details of the study randomization, including randomization date and time, randomized treatment, and actual treatment, will also be included within a subject listing. A listing summarizing all COVID-19-related discontinuations and protocol deviations will be generated as well.

